4.4.6 Left Ventricular Ejection Fraction

All patients will require evaluation of LVEF at screening and Cohorts A and B will require subsequent evaluations of LVEF.

Evaluation of LVEF by ECHO or MUGA scan must be performed at the following timepoints:

- Screening
- Cycle 2, Day 1 \pm 1 week
- Day 1 of every three treatment cycles thereafter, starting at Cycle 5 (\pm 2 weeks)
- The treatment discontinuation visit evaluation of LVEF does not need to be performed at the treatment discontinuation visit if an evaluation has been performed within the last 12 weeks, and there are no clinically significant findings and/or changes from baseline.
- All patients restarting treatment with a dose reduction of cobimetinib because of a decrease in LVEF should have LVEF measurements taken after approximately 2, 4, 10, and 16 weeks, and then resume monitoring LVEF every three treatment cycles.

Any patient who develops clinical signs or symptoms suspicious of cardiac failure should undergo an LVEF assessment. Evaluation of LVEF must be performed by the same method (ECHO or MUGA scan) for each patient. It is strongly encouraged that the same laboratory and operator perform ECHO/MUGA scans for each patient. Investigators

must be aware of local institution regulations regarding repeat MUGA scans. The repeat administration of radioisotopes is limited in some nuclear medicine laboratories, and some patients in this study could require monitoring on four or more occasions.

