5.1.1.1.3 Left Ventricular Dysfunction

Decreases in LVEF from baseline have been reported in patients receiving cobimetinib. Left ventricular dysfunction may occur with signs and symptoms of cardiac failure, or reduction in LVEF events may be asymptomatic.

Left ventricular dysfunction has been characterized in Study GO28141. The study incorporated prospective serial LVEF evaluations in all patients. With active surveillance, measured Grade 2 or 3 reductions in LVEF were observed more frequently in patients treated with cobimetinib plus vemurafenib than placebo plus vemurafenib (8.5% vs. 3.7%, respectively). Of the patients treated with cobimetinib plus vemurafenib, 2 patients (0.8%) had symptomatic reduction in LVEF and the remaining patients were asymptomatic. Most LVEF reduction events in patients on cobimetinib plus vemurafenib (62%) improved or resolved with management according to dose modification guidelines (see in Section [5.1.3.3](#)).

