5.1.3 Management of Patients Who Experience Specific Adverse Events

5.1.3.1 Cobimetinib Dose Modifications

General dose modifications for cobimetinib are provided in [Table 5](#). Dose modifications for specific adverse events are provided in [Table 6](#).

Table 5 Recommended Cobimetinib Dose Modifications

Grade (NCI CTCAE)	Recommended Cobimetinib Dose
Grade 1 or Grade 2 (tolerable)	No dose reduction. Maintain cobimetinib at the same dose of 60 mg QD (3 tablets)
Grade 2 (intolerable) or Grade 3 or 4 (any)	
First appearance	Interrupt treatment until Grade \leq 1, restart treatment at 40 mg QD (2 tablets)
Second appearance	Interrupt treatment until Grade \leq 1, restart treatment at 20 mg QD (1 tablet)
Third appearance	Consider permanent discontinuation.

NCI CTCAE=National Cancer Institute Common Terminology Criteria for Adverse Events;
QD=once daily.

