5.1.3.3 Management of Cobimetinib- and Atezolizumab-Specific Adverse Events

Toxicities associated or possibly associated with cobimetinib plus atezolizumab treatment should be managed according to standard medical practice. See [Appendix 8](#) for management of adverse events related to atezolizumab.

For management of cobimetinib- and atezolizumab-specific toxicities, including IRRs, gastrointestinal toxicity, dermatologic toxicity, hepatotoxicity, pulmonary toxicity, potential eye toxicity, reductions in LVEF from baseline, rhabdomyolysis, elevated CPK, and hemorrhage, see [Table 6](#).

Table 6 Guidelines for Management of Patients Who Experience Specific Adverse Events (Cobimetinib and Atezolizumab)

Event	Action to Be Taken

General guidance for dose modifications and treatment delays and discontinuation
	
 • There will be no dose modifications for atezolizumab. • If atezolizumab is withheld and corticosteroids are initiated for an atezolizumab-related toxicity, corticosteroids must be tapered over ≥ 1 month to ≤ 10 mg/day oral prednisone or equivalent before atezolizumab can be resumed.^{a, b, c} 
The dose of cobimetinib can be reduced by 20 mg (one dose level) up to two times (i.e., from 60 mg to 40 mg and then from 40 mg to 20 mg). If further dose reduction is indicated after two dose reductions, the patient must discontinue cobimetinib but may continue treatment with atezolizumab at the investigator's discretion.
 
 • If atezolizumab is discontinued, treatment with cobimetinib may be continued at the investigator's discretion and after discussion with the Medical Monitor. • If cobimetinib is withheld for > 28 days because of toxicity, the patient should be discontinued from cobimetinib, unless resumption of treatment is approved by the Medical Monitor after discussion with the investigator. • If atezolizumab is withheld for > 105 days because of toxicity, the patient should be discontinued from atezolizumab, unless resumption of treatment is approved by the Medical Monitor after discussion with the investigator.

IRRs, anaphylaxis, and hypersensitivity reaction
	
 • Guidelines for management of IRRs are provided in Appendix 8. • For anaphylaxis precautions, see Appendix 7. • For severe hypersensitivity reactions, permanently discontinue all study treatment.

IRR=infusion-related reaction.

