Table 6 Guidelines for Management of Patients Who Experience Specific Adverse Events (Cobimetinib and Atezolizumab) (cont.)

Event	Action to Be take
Pulmonary events	
General guidance	Mild-to-moderate events of pneumonitis have been reported with atezolizumab and cobimetinib. All pulmonary events should be thoroughly evaluated for other commonly reported etiologies such as pneumonia/infection, lymphangitic carcinomatosis, pulmonary embolism, heart failure, chronic obstructive pulmonary disease, or pulmonary hypertension. For events concerning for pneumonitis, consider comprehensive infectious evaluation including viral etiologies.
Pneumonitis, Grade 1 (asymptomatic)	
 • Continue atezolizumab and cobimetinib. • Re-evaluate on serial imaging. • Consider patient referral to pulmonary specialist.
Pneumonitis, Grade 2	
 • Withhold atezolizumab and cobimetinib. • Refer patient to pulmonary and infectious disease specialists and consider bronchoscopy or BAL. • If bronchoscopy is consistent with immune-related etiology, initiate treatment with 1–2 mg/kg/day oral prednisone or equivalent. • Resume atezolizumab and cobimetinib if event resolves to Grade 1 or better within 105 days.^{a, b} • Permanently discontinue atezolizumab and cobimetinib and contact Medical Monitor if event does not resolve to Grade 1 or better within 105 days.^{a, b, c} • For recurrent events, treat as a Grade 3 or 4 event.
Pneumonitis, Grade 3 or 4	
 • Permanently discontinue atezolizumab and cobimetinib.^c • Refer patient to pulmonary and infectious disease specialists and consider bronchoscopy or BAL. • If bronchoscopy is consistent with immune-related etiology, initiate treatment with 1–2 mg/kg/day oral prednisone or equivalent. • If pulmonary event does not improve within 48 hours or worsens, consider adding an immunosuppressive agent (e.g., infliximab, cyclophosphamide, IVIg, or mycophenolate). • If event resolves to Grade 1 or better, taper corticosteroids over ≥ 1 month.

BAL = bronchoscopic alveolar lavage; IVIg = intravenous immunoglobulin.

^a If corticosteroids have been initiated, they must be tapered over ≥ 1 month to ≤ 10 mg/day oral prednisone or equivalent before atezolizumab can be resumed.

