Table 6 Guidelines for Management of Patients Who Experience Specific Adverse Events (Cobimetinib and Atezolizumab) (cont.)

Event		Action to Be Taken		
LVEF Decrease from Baseline				
Patient	LVEF Value	Recommended Action with Cobimetinib and Atezolizumab	LVEF Value following Treatment Break	Recommended Cobimetinib Daily Dose
Asymptomatic	≥ 50% (or 40%–49% and < 10% absolute decrease from baseline)	Continue atezolizumab and cobimetinib at current dose.	NA	NA
	< 40% (or 40%–49% and ≥ 10% absolute decrease from baseline)	Interrupt cobimetinib treatment for 2 weeks. Continue atezolizumab as clinically indicated.	< 10% absolute decrease from baseline	First occurrence: 40 mg
				Second occurrence: 20 mg
				Third occurrence: permanent discontinuation
< 40% (or ≥ 10% absolute decrease from baseline)	Permanent discontinuation			
Symptomatic	NA	Interrupt cobimetinib treatment for 4 weeks.	Asymptomatic and < 10% absolute decrease from baseline	First occurrence: 40 mg
				Second occurrence: 20 mg
				Third occurrence: permanent discontinuation
		Consider withholding atezolizumab. Discuss with Medical Monitor regarding resumption of atezolizumab.	Asymptomatic and < 40% (or ≥ 10% absolute decrease from baseline)	Permanent discontinuation
Cardiology consultation is strongly recommended.	Symptomatic regardless of LVEF	Permanent discontinuation		

LVEF = left ventricular ejection fraction; NA = not applicable.

Table 6 Guidelines for Management of Patients Who Experience Specific Adverse Events (Cobimetinib and Atezolizumab) (cont.)

Event	Action to Be Taken
Rhabdomyolysis or CPK elevation	
General guidance	
 • Rule out cardiac cause (check electrocardiogram, serum cardiac troponin, and CPK-isoforms M and B fraction) and rule out rhabdomyolysis (clinical examination; serum creatinine, potassium, calcium, phosphorus, uric acid, and albumin; and urine myoglobin). • Assess patient for any history of strenuous physical activity, blunt trauma, or recent intramuscular injections.
For Grade ≤ 3 CPK elevations that are asymptomatic and deemed not clinically significant	
 • Cobimetinib and atezolizumab dosing does not need to be modified or interrupted to manage asymptomatic Grade ≤ 3 CPK elevations. • Recheck CPK at least once a week.

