For Grade 4 CPK elevations that are asymptomatic and deemed not clinically significant	
 • Interrupt cobimetinib and atezolizumab treatment. • If improved to Grade ≤ 3 within 4 weeks, restart cobimetinib at a dose reduced by 20 mg, if clinically indicated. • If CPK elevations do not improve to Grade ≤ 3 within 4 weeks following dose interruption, permanently discontinue cobimetinib treatment. • Resumption of atezolizumab may be considered in patients who are deriving benefit.
Rhabdomyolysis or symptomatic CPK elevations	
 • Interrupt cobimetinib and atezolizumab treatment. • If severity is improved by at least one grade and symptoms resolve within 4 weeks, restart cobimetinib at a dose reduced by 20 mg, if clinically indicated. • If rhabdomyolysis or symptomatic CPK elevations do not improve within 4 weeks, permanently discontinue cobimetinib treatment • Resumption of atezolizumab may be considered in patients who are deriving benefit after discussion with the Medical Monitor.

CPK = creatine phosphokinase.

Table 6 Guidelines for Management of Patients Who Experience Specific Adverse Events (Cobimetinib and Atezolizumab) (cont.)

Event	Action to Be Taken
Hemorrhage	
Grade 3 hemorrhage	
 Interrupt cobimetinib treatment. There are no data on the effectiveness of cobimetinib dose modification for hemorrhage events. Clinical judgment should be applied when considering restarting cobimetinib treatment. Continue atezolizumab treatment.
Grade 4 hemorrhage or any grade cerebral hemorrhage	
 Interrupt cobimetinib treatment. Permanently discontinue cobimetinib for hemorrhage events attributed to cobimetinib. Continue atezolizumab treatment.
Grade 3 or 4 or intolerable Grade 2 treatment-related toxicities not described above and in Table 5 (dose modifications for cobimetinib)	
 Withhold all study treatment. If event resolves to Grade 1 or better within 105 days, resume atezolizumab at fixed dose. If not, permanently discontinue atezolizumab.^{a, b, c} If event resolves to Grade 1 or better within 28 days, resume cobimetinib with dose reduced by one level. If not, permanently discontinue cobimetinib.

^a If corticosteroids have been initiated, they must be tapered over ≥ 1 month to ≤ 10 mg/day oral prednisone or equivalent before atezolizumab can be resumed.

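### The Table 6 LVEF rows set the cobimetinib restart dose by LVEF occurrence alone; for a patient already at 20 mg this conflicts with the table's own general guidance, and no text says which governs

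*Combined protocol and SAP*

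**What the plan says.** Table 6 has two LVEF rows that end in a restart, one asymptomatic and one symptomatic. In both, once LVEF has recovered to less than a 10% absolute decrease from baseline (and symptoms have gone, in the symptomatic row), the recommended cobimetinib daily dose depends on the occurrence: "First occurrence: 40 mg", 20 mg at the second, permanent discontinuation at the third. Neither row refers to the dose being taken when the event occurred.

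The general guidance row that opens Table 6 works relative to the current dose: "The dose of cobimetinib can be reduced by 20 mg (one dose level) up to two times". It then closes the ladder: "If further dose reduction is indicated after two dose reductions, the patient must discontinue cobimetinib".

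Section 5.1.3.1 routes particular toxicities to Table 6 ("Dose modifications for specific adverse events are provided in" that table). Table 5, in the same section, covers general modifications and also uses absolute doses: 40 mg after a first appearance, 20 mg after a second, and consideration of permanent discontinuation at a third.

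Section 4.4.6 assumes that the LVEF restart is at a lower dose. Its extra LVEF checks at about 2, 4, 10 and 16 weeks apply to "All patients restarting treatment with a dose reduction of cobimetinib because of a decrease in LVEF".

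**The concern.** The ladder of 40 mg, 20 mg, stop is coherent for a patient who starts at 60 mg and is reduced only for LVEF. Cobimetinib is also reduced for many other toxicities in this protocol, so a first LVEF event can occur in a patient already at 40 mg or 20 mg. At 20 mg the row's dose is above the dose at which the cardiac event occurred, while the general guidance points to discontinuation.

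What is at stake is dosing after a cardiac toxicity in patients who have already needed two reductions, and the chance that sites handle the same patient differently. A side effect is that a patient restarted at an unchanged or higher dose falls outside the wording that triggers the extra LVEF checks in Section 4.4.6.

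**Working it through.** No sample-size or power figure is involved, so there is no stated figure to reproduce. The check is to list the dose states and compare the two rules.

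**Inputs.** Starting dose 60 mg (Section 4.2.2.1). Other toxicities step the dose down by 20 mg, from 60 to 40 to 20 mg (Table 6, general guidance). The LVEF rows are followed literally: first event 40 mg, second 20 mg, third stop. LVEF is assumed to recover enough for a restart, since otherwise the rows require permanent discontinuation.

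**Reachable states.** Change = restart dose minus dose at event. The last column applies one step down from the dose at the event, stopping if already at 20 mg or at the third occurrence.

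| LVEF occurrence | Dose at event | LVEF row, literal | Change | One step down |
|---|---|---|---|---|
| 1st | 60 mg | 40 mg | −20 mg | 40 mg |
| 1st | 40 mg | 40 mg | 0 | 20 mg |
| 1st | 20 mg | 40 mg | +20 mg | stop |
| 2nd | 40 mg | 20 mg | −20 mg | 20 mg |
| 2nd | 20 mg | 20 mg | 0 | stop |
| 3rd | 20 mg | stop | – | stop |

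Three states behave as the ladder intends. Two leave the dose unchanged. One raises it from 20 to 40 mg, which is 20/20 = 100%. A patient reduced only for LVEF passes through 60, 40, 20 and stop under either rule.

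**Comparison with other rows.** Nine Table 6 rows word the restart relative to the current dose: diarrhea Grade 2 (intolerable) or 3, colitis Grade 2, colitis Grade 3, dermatologic Grade 3, AST/ALT with raised bilirubin, serous retinopathy, Grade 4 CPK, rhabdomyolysis or symptomatic CPK, and the catch-all. The two CPK rows make the reduction conditional on clinical indication. Other rows state no restart dose at all. For Grade 2 pneumonitis the row says "Resume atezolizumab and cobimetinib if event resolves to Grade 1 or better within 105 days", and for Grade 3 hemorrhage "Clinical judgment should be applied when considering restarting cobimetinib treatment". Restarting at an unchanged dose therefore breaks no explicit rule, and the two unchanged-dose states are not errors in themselves. The conflict lies in the state that starts at 20 mg.

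**Rough scale.** Section 5.1.1.1.3 gives, for cobimetinib plus vemurafenib in Study GO28141, Grade 2 or 3 LVEF reductions in 8.5% of patients, with 62% of events improved or resolved. Applied to the 102 patients in Cohorts A and B:

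- expected with an LVEF reduction: 102 × 0.085 = 8.67
- of which recovering: 8.67 × 0.62 = 5.38

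The share already at 20 mg for other reasons is not in the documents. Assumed shares of 5%, 10% and 25% give 5.38 × 0.05 = 0.27, 5.38 × 0.10 = 0.54 and 5.38 × 0.25 = 1.3 patients. The partner drug differs, and neither the grading nor the recovery definition matches the row's thresholds. These figures show order of magnitude only. They count patients who would reach the state, not patients who would be given 40 mg.

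**The case against.** The strongest reply is that the LVEF rows should not be read apart from the table they stand in. The general guidance provides only for downward steps and ends in discontinuation, Section 4.4.6 calls the LVEF restart a reduction, and no text provides for re-escalating cobimetinib. Together these point to stopping in a patient already at 20 mg. This much stands: a reader might infer that the protocol directs investigators to double the dose after a cardiac event, and the documents do not support that.

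It does not remove the conflict. The general guidance is permissive about reductions, and its stop rule applies only when a further reduction is indicated; at 20 mg the LVEF row indicates 40 mg instead. Section 4.4.6 shows intent but sets no dose. Section 5.1.3.1 sends the reader to Table 6, where both the general and the specific row are found, without saying which prevails.

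The conflict would also disappear if occurrence counted every dose-reducing toxicity. But the rows sit under the LVEF heading and nothing says so.

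Two further points stand. Table 5 uses the same absolute format, so the LVEF rows are not a lone exception, and correcting them alone would leave the broader instance in place. And the column is headed as a recommendation in a table of guidelines, with dosing dependent on an acceptable clinical assessment (Section 4.4). An investigator is free to go lower, although the row does not say to.

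**Conclusion.** The point holds as an internal inconsistency. The absolute LVEF restart doses presume that all earlier reductions were for LVEF. For a first LVEF event at 20 mg they cannot be reconciled with the general guidance or Section 4.4.6, and no precedence is stated.

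The severity is minor. It is a safety-wording matter confined to Cohorts A and B, since Cohort C receives no cobimetinib, and it has no effect on ORR or DCR. On the borrowed rates and assumed shares above, about one patient or fewer would reach the conflicting state. That size depends mainly on the unknown share at 20 mg, so it should not be quoted as an estimate. The existence of the conflict depends only on the text.

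**What to change.** In both LVEF rows, replace the restart doses with: *restart one dose level (20 mg) below the dose at the time of the event; permanently discontinue if already at 20 mg or at the third occurrence*. Align the Table 5 restart doses so that no restart exceeds the dose at the event.

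The cost is a few words at the next amendment, with no new visits, patients or procedures. There is a small clinical downside: a few patients already reduced for other toxicities would step down or stop earlier than the present rows imply. A first event at 40 mg would restart at 20 mg, and a second event at 20 mg would end cobimetinib. That is consistent with the general guidance row.

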 - Patients with a history of isolated elevation in prostate-specific antigen in the absence of radiographic evidence of metastatic prostate cancer are eligible for the study.
- Treatment with any anti-cancer agent 14 days prior to Cycle, Day 1 other than aPD-1 based therapy
- Adverse events from prior anti-cancer therapy that have not resolved to Grade ≤ 1
 - Clinically stable patients with manageable immune-related adverse events resulting from prior cancer immunotherapy may be eligible for the study after discussion with and approval by the Medical Monitor.

- For Cohort C, specific exclusion criteria include any prior anti-cancer therapy for advanced melanoma

Ocular Exclusion Criteria (Cohorts A and B)

- History of serous retinopathy
- History of retinal vein occlusion (RVO)
- Evidence of ongoing serous retinopathy or RVO at baseline

Cardiac Exclusion Criteria (Cohorts A and B)

- History of clinically significant cardiac dysfunction, including the following:
 - Unstable angina, or new-onset angina within 3 months before initiation of study treatment
 - Symptomatic congestive heart failure, defined as New York Heart Association Class II or higher
 - Myocardial infarction within 6 months before initiation of study treatment
 - Unstable arrhythmia
 - History or presence of an abnormal ECG that is clinically significant in the investigator's opinion, including complete left bundle branch block, second- or third-degree heart block, or evidence of prior myocardial infarction
 - Left ventricular ejection fraction below the institutional lower limit of normal or below 50%, whichever is lower

Central Nervous System Exclusion Criteria

- Untreated or actively progressing central nervous system (CNS) lesions (carcinomatous meningitis)
 - Patients with stable and asymptomatic CNS metastases are eligible, if they meet all of the following:
 - Measurable disease, per RECIST v1.1, must be present outside the CNS.
 - All known CNS lesions are clinically stable.
 - CNS lesions have not been treated with whole-brain radiotherapy, except in patients who underwent definitive resection of or stereotactic therapy for all radiologically detectable parenchymal brain lesions.
 - Absence of interim progression must be confirmed by radiographic study within 4 weeks before initiation of study treatment. If new CNS metastases are suspected during the screening period, a confirmatory radiographic study is required before initiation of study treatment.

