4.1.2.3 Cardiac Exclusion Criteria (Cohorts A and B)

- History of clinically significant cardiac dysfunction, including the following:
 - Unstable angina, or new-onset angina within 3 months before initiation of study treatment
 - Symptomatic congestive heart failure, defined as New York Heart Association Class II or higher
 - Myocardial infarction within 6 months before initiation of study treatment
 - Unstable arrhythmia
 - History or presence of an abnormal ECG that is clinically significant in the investigator's opinion, including complete left bundle branch block, second- or third-degree heart block, or evidence of prior myocardial infarction
 - LVEF below the institutional lower limit of normal or below 50%, whichever is lower

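### Table 6, LVEF: after the treatment break, an LVEF below 40% with a fall of under 10 points meets both the restart row and the permanent-stop row

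*Combined protocol and SAP*

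**What the plan says.** Table 6 first sorts patients by LVEF on treatment.

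- An asymptomatic patient continues at "≥ 50% (or 40%–49% and < 10% absolute decrease from baseline"). Otherwise cobimetinib is interrupted for 2 weeks.
- A symptomatic patient has cobimetinib interrupted for 4 weeks.

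After the break, LVEF is read again.

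- **Asymptomatic branch.** The restart row reads "< 10% absolute decrease from baseline First occurrence: 40 mg", with 20 mg at the second occurrence and permanent discontinuation at the third. The stop row reads "< 40% (or ≥ 10% absolute decrease from baseline").
- **Symptomatic branch, once symptoms have resolved.** The restart row reads "Asymptomatic and < 10% absolute decrease from baseline", with the same dose steps. The stop row reads "Asymptomatic and < 40% (or ≥ 10% absolute decrease from baseline").

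Neither the table nor the surrounding text says which row prevails if both are met.

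Baseline LVEF in Cohorts A and B is governed by Section 4.1.2.3 and the matching synopsis criterion, which exclude "LVEF below the institutional lower limit of normal or below 50%, whichever is lower".

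**The concern.** The stop row uses two tests joined by *or*: an absolute threshold of 40% and a fall of 10 points or more. The restart row uses only the second. A patient below 40% whose fall is under 10 points is therefore sent to restart by one row and to permanent discontinuation by the other.

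This looks like a slip. The pre-break continue row carries the 40% floor, and the restart rows leave it out. As written, a patient can satisfy the restart row with no recovery at all: an LVEF of 38% that triggered the interruption, and is still 38% after it, qualifies if the baseline was 47%.

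What is at stake is a dosing rule. Section 5.1.1.1.3 places left ventricular dysfunction among the important identified risks of cobimetinib. It reports Grade 2 or 3 LVEF reductions in 8.5% of patients on cobimetinib plus vemurafenib against 3.7% on placebo plus vemurafenib in Study GO28141. The patients exposed to the conflict are those who enter with the lowest LVEF. Two investigators could read the same result and act in opposite ways, each pointing to a row of the table.

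**Working it through.** There is no sample-size or power figure to reproduce. The check is whether the rows divide the possible results cleanly.

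**Inputs.** Let b be baseline LVEF and p post-break LVEF, both in percentage points, with fall d = b − p. From Table 6:

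- Restart: d < 10
- Stop: p < 40 or d ≥ 10

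From Section 4.1.2.3, b is at least the smaller of the institutional lower limit of normal (L) and 50. The documents do not give L, so I assume values from 40% to 55%.

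**Where both rows apply.** A result meets both rows exactly when p < 40 and d < 10. Then b = p + d < 40 + 10 = 50. The overlap is empty for every baseline of 50% or more and can be reached only below 50%. No result falls outside both rows.

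**Example.** With b = 47 and p = 38, d = 47 − 38 = 9. Since 9 < 10, restart is met. Since 38 < 40, stop is met.

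**Whole-number count.** For a given b from 40 to 48, the overlapping values of p run from b − 9 to 39, which is 39 − (b − 9) + 1 = 49 − b values. Summing from b = L to 48 gives (49 − L)(50 − L)/2 pairs.

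| Assumed lower limit L | Pairs (b, p) meeting both rows |
|---|---|
| 40% | 9 × 10 / 2 = 45 |
| 42% | 7 × 8 / 2 = 28 |
| 45% | 4 × 5 / 2 = 10 |
| 47% | 2 × 3 / 2 = 3 |
| 48% | 1 × 2 / 2 = 1 |
| 49% to 55% | 0 |

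These are counts of possible readings, not of patients or probabilities. They show only how fast the overlap shrinks as the limit rises. The highest affected whole-number baseline is 48%, with 39% after the break. With decimals, the exact bound is b < 50: for example, b = 49 and p = 39.5 gives d = 9.5 and meets both rows.

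**Comparison with the pre-break rows.** In whole numbers, continue is p ≥ 50, or p from 40 to 49 with d < 10. Interrupt is p < 40, or p from 40 to 49 with d ≥ 10. These give 0 overlaps and 0 gaps.

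**After the change.** With restart defined as p ≥ 40 and d < 10, over b from 40 to 80 and p from 10 to 80, 0 pairs meet both rows and 0 meet neither.

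**The case against.** The strongest reply is that the intent can be read from the table. For a baseline of 50% or more, an LVEF below 40% is always a fall of more than 10 points, so the 40% term in the stop row has work to do only in the disputed zone. Reading the restart row as governing would leave that term without any function. That inference is sound, and stopping is very probably what was meant. But it has to be worked out; the restart cells do not say it.

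The second reply is reach. No site limit is given, so nothing in the documents shows that a patient with a baseline below 50% will enrol. This stands, and it is why the point is minor. It does not make the case impossible: the criterion takes whichever value is lower, and Section 9.4 plans about 60 centres globally.

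The third reply is that other safeguards exist. Patients are assessed for toxicity before each dose (Section 4.4). Treatment must stop for any medical condition judged to jeopardize safety (Section 4.5.3). Symptomatic heart failure or a Grade ≥ 3 LVEF reduction must be reported within 24 hours (Section 5.2.3). Cardiology consultation is strongly recommended in the symptomatic branch. Patients restarted at a reduced dose after an LVEF decrease "should have LVEF measurements taken after approximately 2, 4, 10, and 16 weeks" (Section 4.4.6). These limit the harm. None settles which row applies, and the repeat LVEF schedule begins only after the drug has been restarted.

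**Conclusion.** The post-break restart and stop rows conflict in both branches of the LVEF table when LVEF is below 40% and the fall is under 10 points. The text is wrong as written, and the matter is one of patient safety, but it is minor. The conflict is confined to patients with a baseline below 50%, at sites whose lower limit of normal is below 50%, and to first and second occurrences, because at the third both rows stop the drug. How often this would arise cannot be estimated, since site limits are not given. No endpoint, estimate or analysis depends on it.

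**What to change.** Add LVEF ≥ 40% as a condition in the two restart cells. In the asymptomatic branch, restart would require LVEF ≥ 40% together with a fall of under 10 points. In the symptomatic branch, it would require absence of symptoms, LVEF ≥ 40% and a fall of under 10 points. Leave the stop rows unchanged. An LVEF below 40% after the break then always means permanent discontinuation, and each result leads to one action.

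Patients with a baseline of 50% or more are managed exactly as now. The cost is a few words in two cells at the next amendment, with no effect on sample size, endpoints or timelines.
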